10.1 Withdrawal

Participants have the right to withdraw consent for participation in any aspect of the trial at any time. The participants' care will not be affected at any time by declining to participate or withdrawing from the trial.

If a participant initially consents but subsequently withdraws from the trial, clear distinction must be made as to what aspect of the trial the participant is withdrawing from. These aspects could be:

- 1. Withdrawal from randomisation to receive either a perineural nerve catheter or not as part of the trial (pre-operatively)
- Withdrawal from continuing to receive local anaesthetic via the perineural nerve catheter for (up to) the first 5 postoperative days as part of the trial (post-operatively)
- 3. Withdrawal from using routinely collected clinical data for the trial (no permission for the research team to look in medical notes to collect health and medications information)

- 4. Withdrawal from 3-month follow-up (no permission to be contacted by a member of the research team to ask questions about health at 3 months)
- 5. Withdrawal from 6-month follow-up (no permission to be contacted by a member of the research team to ask questions about health at 6 months)
- 6. Withdrawal from contacting alternative contact for 3-month follow-up (no permission to be contacted by a member of the research team to ask questions about health at 3 months)
- 7. Withdrawal from contacting alternative contact for 6-month follow-up (no permission to be contacted by a member of the research team to ask questions about health at 6 months)
- 8. Withdrawal from the research team communicating with their GP
- 9. (If applicable) Withdrawal from the optional use of information collected by NHS digital and other NHS central bodies for longer term follow up
- 10. (If applicable) Withdrawal from the optional Follow-Up Study Within A Trial (SWAT) (to be shown an additional video)
- 11. (If applicable) Withdrawal from the optional qualitative interview (interview about health and experiences in the trial)
- 12. Withdrawal of use of data already collected. (Does the participant wish us to destroy trial data collected prior to their withdrawal?)
 - 13. Withdrawal of consent to all of the above

The withdrawal of participant consent shall not affect the trial activities already carried out and the use of data collected prior to participant withdrawal. The use of the data collected prior to withdrawal of consent is based on informed consent before its withdrawal. Furthermore, it is important to collect safety data ongoing at the time of withdrawal, especially if the participant withdraws because of a safety event. There is specific guidance on this contained in the PIS but briefly: If a participant wishes to stop taking part in the trial completely, they will need to be seen one last time for an assessment and tests. If the participant is suffering a serious reaction to the trial treatment when they decide to stop, collection of information about them will need to continue for as long as the reaction lasts.

A participant may withdraw or be withdrawn from trial treatment for the following reasons:

- Intolerance to trial medication
- Serious toxicity
- > Withdrawal of consent for treatment by the participant

Any alteration in the participant's condition which justifies the discontinuation of the treatment in the Investigator's opinion

In all instances participants who consent and subsequently withdraw should complete a withdrawal of consent form (see Withdrawal Form in trial pack) or the withdrawal form should be completed on the participant's behalf by the researcher/clinician based on information provided by the participant. This withdrawal form should be sent to the PLACEMENT TM. Any queries relating to potential withdrawal of a participant should be forwarded to the PLACEMENT TM.

10.2 Lost to Follow-Up

Participants will be identified as lost to follow-up if it is not possible to contact them directly or designated additional contact person for 3- and 6-month follow-up. At enrolment, participants will be asked to provide details of an alternative contact person (e.g. close friend, relative or carer) who they are happy for members of the research team to contact for follow-up if the participant themselves cannot be contacted. Participants will also consent to the research team communicating with their GP if required. All outcome data will be collected, and the primary analysis will be performed on an intention to treat basis for protocol non-adherers.

11 Trial Intervention

11.1 Treatment(s)

In participants randomised to the intervention arm, a PNC is inserted adjacent to the cut end of the major nerve (either sciatic nerve for AKAs, or tibial nerve for BKA/TKAs) and tunnelled externally before being connected to a local anaesthetic infusion device delivering local anaesthetic via an elastomeric or electronic pump for up to five days. Participants randomised to the control arm will not have a PNC inserted during their MLLA.

The placement of the PNC is rapid to learn for surgeons who are not already trained in the technique. All surgeons involved in placing a PNC will undergo training according to the Standard Operating Procedure (SOP) for insertion of the perineural catheter and management of local anaesthetic infusion, to ensure the technique used is as homogenous as possible. An accompanying training presentation will illustrate the intervention. The important points are covered in Section 11.1.1 below.

All participants in both arms will receive 'best care' personalised pre-, intra-, and postoperative analgesia at the discretion of the treating medical teams. This may include patient-controlled, IV, and/or oral analgesia. Ultrasound-guided nerve blocks and catheters (e.g., to the femoral nerve), and injections of local anaesthetic directly into/around the nerve at the time of surgery, are permitted in either arm.

11.1.1 Placement of the Perineural Catheter

Placement of a PNC takes 5-10 minutes (38) and requires no further dissection over and above what is already undertaken for lower limb amputations. Intra-operatively, the sciatic nerve (for AKA) or tibial nerve (for BKA/TKA) is identified and divided long. An epidural catheter (typically 20G, 0.85mm diameter) is used as the PNC and placed in the perineural space after the limb has been removed. Epidural catheter packs come with a Tuohy needle; a non-coring needle with a slight curve at its tip which causes a catheter passed through the needle to exit at approximately 45 degrees which is used to place the catheter in the correct location. The Tuohy needle is first placed in the appropriate space, either in the extraneural space (i.e., perineural space), or (if the epineurium is deliberately entered with the needle) in the intraneural space. The fenestrated end of the epidural catheter is advanced along the needle so to lie approximately 10 cm cranial from the cut end, and the needle withdrawn leaving the catheter in place. A suitable exit site for the catheter on the lateral aspect of the amputation stump is selected, and the Tuohy needle passed through the skin (external to internal) at this point. The free end of the epidural catheter is then passed through the needle, which is then withdrawn to leave the catheter exiting the wound. The nerve is transected sharply under gentle tension, to allow the cut end of the nerve to retract away from the wound to reduce the incidence of neuroma formation, as is standard surgical practice (57). The amputation is completed, and the epidural catheter secured to the skin with a silk suture or dressing. The epidural infusion system is then connected to the end of the catheter, is typically flushed with a local anaesthetic bolus, and is then ready for connection to the local anaesthetic infusion device.

11.1.2 Local Anaesthetic Infusion Devices

Two different local anaesthetic infusion devices may be used: an electronic infusion pump or elastomeric reservoir ball. These are both licensed for administration of peripheral local anaesthetic infusions.

11.1.2.1 Electronic Infusion Pumps

Electronic infusion pumps, similar to epidural infusion pumps, provide a continuous infusion of fluid to the PNC. Nursing staff are familiar with the machines used and the type of records such pumps require in nursing notes (volume given and remaining, infusion rate). The infusion is typically stored in a 250 ml bag, and both are mounted on a 'drip stand' or equivalent by the patient's bed. Any breaks in infusion of <60 minutes will be considered as continuous to allow for changeover of bags. The rate will be variable as described below in Section 11.4. Additional boluses of local anaesthetic may be used, but the total dose in 24 hours must be kept below the amount recommended in the SmPCs.

11.1.2.2 Elastomeric Reservoir Ball System

Elastomeric reservoir balls provide an automated continuous controlled infusion of local anaesthetic for use with the PNC in the postoperative period. They are widely used in a range of surgical settings. Pressure is generated by the force of the stretched elastomer, which has been shown to result in constant infusion rates within a 15% tolerance (58).

Once attached to the PNC, the elastomeric reservoir balls require no input to undertake their function. The infusion device has markings which can be used to ascertain how much volume has been infused, and thereby check the infusion rate. During the trial, the amount (and concentration) of drug infused will be recorded daily to ensure consistent infusion rates. Additional boluses of local anaesthetic may be used, but the total dose in 24 hours must be kept below the amount recommended in the SmPCs.

11.2 Treatment Supply and Storage

The IMPs are typically available and stored in the theatre department. They are stored at room temperature/below 25°C, in clearly labelled bags similar to other infusion fluid bags. They are stable with a long shelf life under standard conditions (room temperature/below 25°C) therefore IMP storage temperature will not be monitored in this trial consistent with Type A clinical trials.

11.3 Treatment Prescribing and Dispensing

For participants randomised to the treatment arm, local procedures will be followed e.g. local anaesthetic infusions prescribed on a specific prescription chart designed for PNCs and dispensed either from the store kept in the theatre complex or directly from the pharmacy department. The batch number of the infusion bag(s) used will be recorded for Trial traceability.

11.4 Dosing Schedule

When devices allowing varying infusion rates are used, infusions will be commenced in theatre and titrated as appropriate by anaesthetists, specialist pain nurses or another appropriate HCPs. Participants will only be permitted to have a single type of IMP for the duration of the trial; use of multiple agents for a single patient is very unusual in clinical practice and would only be required due to supply issues. The choice of IMP is down to the treating clinical team.

The total dose and rates of the IMPs not to be exceeded are:

- Levobupivacaine hydrochloride, typically in a 0.125 to 0.25% solution, delivered at a rate of 1 to 15 mg/hour. Maximum dose over 24 hours should not exceed 400 mg.
- Ropivacaine hydrochloride, typically in a 0.2% solution, delivered at a rate of 10 to 20mg/hour.
 Maximum dose over 24 hours should not exceed 800 mg.
- Bupivacaine hydrochloride, typically in a 0.1 to 0.25% solution. Maximum dose over 24 hours should not exceed 400 mg.

The maximum doses should be reduced for patients who are acutely ill, elderly, debilitated or weigh <60kg. Note that the 24-hour dose must be calculated to include one-off injections at the time of anaesthesia/surgery, and bolused local anaesthetic doses.

11.5 Dose Modification to Avoid Toxicity

To avoid the risk of toxicity in obese participants, dose calculations that include weight should be calculated using the participant's ideal weight, rather than actual weight. Manufacturers advise caution in using Bupivacaine and Ropivacaine in the presence of significant renal impairment. Manufacturers advise caution in using Levobupivacaine, Bupivacaine, and Ropivacaine in the presence of significant hepatic impairment, cardiovascular disease, complete heart block, epilepsy, hypovolaemia, impaired cardiac conduction, impaired respiratory function, myasthenia gravis, and shock. Manufacturers advise to consider a reduction in the dose of Levobupivacaine, Bupivacaine, and Ropivacaine in debilitated and/or elderly patients.

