11.7 Prohibited Medications and Interaction with Other Drugs

Caution must be used in the administration of other local anaesthetics or agents structurally related to amide-type local anaesthetics, e.g., certain antiarrhythmics, such as lidocaine and mexiletine, since the systemic toxic effects are additive. While patients already taking these medications at time of enrolment will be excluded, use of them postoperatively must be undertaken with caution but is not specifically prohibited. Full information is available from the SmPC for Levobupivacaine, Ropivacaine and Bupivacaine which are attached as an appendix to this protocol.

There are no other specific prohibited medications, however caution must be used in the administration of local anaesthetic for other purposes to ensure that a maximum dose of the local

anaesthetic does not exceed recommended dose rates. The maximum doses should be reduced for patients who are acutely ill, elderly, debilitated or <60kg.

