11.8 Accountability Procedures

No medications or associated equipment or consumables are being provided to sites as part of the trial, and therefore, sites are expected to use their own stock. No CTR accountability, recall and disposal procedures are required as described in the PLACEMENT IMP Management Plan. Sites should follow local governance for the off-license use of Levobupivacaine, Ropivacaine and Bupivacaine (i.e., via PNC). The PLACEMENT Trial SOP for insertion of the PNC should also be followed.

Local anaesthetic will be infused for up to five days postoperatively, and therefore, continuation of the IMP after completion of the trial is not applicable. Once participation in the trial has ended, any additional care is not expected to differ from what is normally expected for patients who have undergone MLLA for PAD +/- diabetes.

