4.2 Posology and method of administration

Levobupivacaine should be administered only by, or under the supervision of, a clinician having the necessary training and experience.

Chirocaine Solution for Infusion is for epidural use only. It must not be used for intravenous administration.

Type of Block	Concentration	Infusion Rate Per Hour	
	mg/ml	ml	mg
Continuous Infusion:			
Post-operative pain management	1.25	10-15	12.5-18.75
Lumbar epidural (analgesia in labour)	1.25	4-10	5-12.5

Careful aspiration before infusion is recommended to prevent intravascular injection. If toxic symptoms occur, the injection should be stopped immediately.

There is limited safety experience with levobupivacaine therapy for periods exceeding 24 hours. In order to minimise the risk for severe neurological complications, the patient and the duration of administration of levobupivacaine should be closely monitored (see section 4.4).

Maximum dose

The maximum dosage must be determined by evaluating the size and physical status of the patient. The maximum recommended dose during a 24 hour period is 400 mg.

For post-operative pain management, the dose should not exceed 18.75 mg/hour, however the accumulated dose for a 24 hour period should not exceed 400 mg. For labour analgesia by epidural infusion, the dose should not exceed 12.5 mg/ hour.

Paediatric population

The safety and efficacy of levobupivacaine in children for pain management has not been established.

Special Populations

Debilitated, elderly or acutely ill patients should be given reduced doses of levobupivacaine commensurate with their physical status.

In the management of post-operative pain, the dose given during surgery must be taken into account.

There are no relevant data in patients with hepatic impairment (see sections 4.4 and 5.2).

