4.3 Contraindications

9/13/22, 2:21 PM

Chirocaine 1.25 mg/ml solution for infusion - Summary of Product Characteristics (SmPC) - print friendly - (emc)

General contraindications related to regional anaesthesia, regardless of the local anaesthetic used, should be taken into account.

Levobupivacaine solutions are contraindicated in patients with a known hypersensitivity to active substance, local anaesthetics of the amide type or any of the excipients listed in section 6.1 (see section 4.8).

Levobupivacaine solutions are contraindicated for intravenous regional anaesthesia (Bier's block).

Levobupivacaine solutions are contraindicated in patients with severe hypotension such as cardiogenic or hypovolaemic shock.

Levobupivacaine solutions are contraindicated for use in paracervical block in obstetrics (see section 4.6).

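### Protocol section 11.5 reports the manufacturers' position on levobupivacaine in shock as caution, but the appended levobupivacaine SmPC contraindicates it in severe hypotension from cardiogenic or hypovolaemic shock

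*Protocol*

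**What the plan says.** Protocol section 11.5 (Dose Modification to Avoid Toxicity) deals with the three permitted agents in one pooled sentence. It opens "Manufacturers advise caution in using Levobupivacaine, Bupivacaine, and Ropivacaine in the presence of significant hepatic impairment" and runs through a list that includes hypovolaemia and closes with "impaired cardiac conduction, impaired respiratory function, myasthenia gravis, and shock". Shock appears there without qualification and with the same weight for all three agents.

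Appendix 1 reproduces the SmPC for levobupivacaine 1.25 mg/ml solution for infusion. Its section 4.3 (Contraindications) states: "Levobupivacaine solutions are contraindicated in patients with severe hypotension such as cardiogenic or hypovolaemic shock".

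The body of the protocol refers to the SmPCs in general terms. Section 11.7 says "Full information is available from the SmPC for Levobupivacaine, Ropivacaine and Bupivacaine which are attached as an appendix to this protocol". Section 11.8 asks sites to follow local governance for the "off-license use of Levobupivacaine, Ropivacaine and Bupivacaine" by the perineural route.

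**The concern.** A caution leaves the decision to the clinician's judgement; a contraindication says not to use the drug. Section 11.5 does not present a perineural rule devised for the trial. It reports what manufacturers say, and for levobupivacaine in severe hypotension from shock that report is weaker than the manufacturer's text bound into the same document.

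At stake is a safety instruction. Emergency amputations are eligible (section 8.1), and infusions given by variable-rate devices are started in theatre (section 11.4), so a participant in this state at the start of infusion is conceivable. A reader of 11.5 would take levobupivacaine to be allowed with care.

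**Working it through.** No arithmetic applies, so the check is a comparison of texts.

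1. **The two statements.** Section 11.5: levobupivacaine, shock, caution. Appendix 1, SmPC section 4.3: levobupivacaine, severe hypotension with cardiogenic and hypovolaemic shock as examples, contraindicated. They overlap where shock brings severe hypotension, and there they differ in strength.

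2. **Is the SmPC line tied to a technique that the trial does not use?** Four lines in SmPC 4.3 open by saying that levobupivacaine solutions are contraindicated. Two name a technique: "Levobupivacaine solutions are contraindicated for intravenous regional anaesthesia" and "Levobupivacaine solutions are contraindicated for use in paracervical block in obstetrics". The other two, on hypersensitivity and on severe hypotension, depend on the patient's condition. The shock line names no route or technique.

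3. **Does the SmPC contain softer wording that 11.5 could be paraphrasing?** Section 4.4 of the SmPC (warnings and precautions) asks for caution in debilitated, elderly or acutely ill patients and in liver disease. It has no caution-level statement on shock that would replace the line in 4.3.

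4. **Does the protocol body state the contraindication elsewhere?**
   - Section 8.2 treats patients as unsuitable after intra-operative instability only if they need ICU with likely sedation beyond 24 hours, or are not expected to survive more than two weeks. Neither item names shock or hypotension.
   - Sections 11.4 and 11.7 call for lower maximum doses in the acutely ill, which still allows use.
   - Section 11.6 requires the infusion to stop when hypersensitivity or toxicity is suspected. It does not address starting levobupivacaine in a patient already in shock.
   - Section 11.7 points to the SmPCs without stating the rule.

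5. **Does the protocol rely on the SmPCs for perineural use?** Yes, for dosing. Sections 11.1.2.1 and 11.1.2.2 keep the 24-hour total below the SmPC amount, and the 400 mg levobupivacaine ceiling in section 11.4 equals the 24-hour maximum in SmPC section 4.2.

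6. **Can 11.5 distinguish between agents?** It already does: its renal impairment sentence covers bupivacaine and ropivacaine only.

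**The case against.** The strongest reply is that the stricter rule is already in the protocol. Appendix 1 is part of the document, section 11.7 directs readers to it, and 11.5 is about dose modification and is not a list of contraindications. It is also a class-level summary: it names conditions, such as myasthenia gravis and complete heart block, that section 4.4 of the appended SmPC does not list, so it need not be a transcription of that source. The SmPC says "Chirocaine Solution for Infusion is for epidural use only", covers only the 1.25 mg/ml strength although section 11.4 allows up to 0.25%, and the trial use is perineural and off licence.

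These points lower the practical risk. They do not make the statement about manufacturers correct, because a general pointer does not cancel a specific contrary sentence and the SmPC line on shock names no route.

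Other safeguards also count. The clinical team chooses the agent (11.4) and may give alternative treatment (9.4), treatment may be stopped when a change in condition justifies it (10.1), and local prescribing procedures and governance apply (11.3, 11.8). A reader might infer from 11.5 that participants in shock are unprotected, or that 11.5 is the working prescribing reference. The documents support neither. What can be said is that none of these provisions states the contraindication.

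**Conclusion.** The inconsistency is real and minor. For levobupivacaine in severe hypotension such as that of cardiogenic or hypovolaemic shock, section 11.5 understates the contraindication in section 4.3 of the SmPC in Appendix 1. The conclusion rests on the two texts alone and assumes no event rate; the documents support no estimate of how often the situation would arise. There is no effect on eligibility, the primary outcome, the sample size of 650 or the analysis.

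Four wider readings are tempting and should be set aside:

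- *That 11.5 is equally wrong for ropivacaine and bupivacaine.* Appendices 2 and 3 appear by title only in the text available, so this cannot be checked.
- *That caution is wrong for all shock, or for hypovolaemia.* The SmPC line concerns severe hypotension. Hypovolaemia without shock, and shock without severe hypotension, are not shown to be misdescribed.
- *That the exclusion criteria need a shock item.* The conflict concerns the use of one of three permitted agents, and the team may choose another.
- *That a new rule for stopping a running infusion is required.* The SmPC line does not spell one out. Sections 10.1 and 11.6 already allow discontinuation and require stopping for suspected toxicity.

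**What to change.** Reword section 11.5 so that its caution wording for levobupivacaine no longer covers this state. Adding a sentence while leaving the list as it stands would put caution and contraindication side by side for the same drug and condition.

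Then add a sentence such as: *Levobupivacaine is contraindicated, and must not be started, in severe hypotension, for example in cardiogenic or hypovolaemic shock (SmPC section 4.3, Appendix 1).*

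Check section 4.3 of the ropivacaine and bupivacaine SmPCs (Appendices 2 and 3) and word 11.5 agent by agent, as its renal impairment sentence already does.

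The cost is a short amendment under section 21.1: TMG review, submission to REC and HRA, to the MHRA if necessary, and an alert to sites. It can be bundled with the next amendment. No change to eligibility, sample size or analysis follows.
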